6.3 Withdrawal of patients

The patients can at any time choose to stop participating in the study without giving any reason for this. If possible, the reason for the patient leaving the study should be recorded. Data collected up to the subject's leaving the study will be used in the analysis of the study.

The investigator can remove a patient from the study due to safety reasons or in case the patient is not able to comply with the protocol.

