All patients will be treated with the study drug rituximab on one single occasion and followed for a total of 1 year. They will have a total of 13 visits (screening prior to inclusion can be divided into more than one visit if necessary) with a clinician or research nurse who is experienced with rituximab and with psychiatric patients. An extensive psychiatric interview will be performed with each patient and his/her next of kin at baseline. We will also review medical records in order to document previous symptomatology and treatment trials. A short video recording is optional. All participants will be examined for psychiatric, neurological and motor symptoms, cognitive functioning, and a range of biomarkers. However only blood sampling and the interview are prerequisites for participation, all other examinations and tests are optional. Prior and post treatment the optional lumbar puncture and fMRI will be performed for further diagnostic evaluation and assessment of blood-brain barrier function. Faeces samples will also be collected prior to treatment and endpoint 1 of this study (optional) as well as gut biopsy prior to treatment (optional). Patients are requested to remain on their standard psychiatric treatment until endpoint 1, and treatment should be stable for the last 1 month prior to baseline. Patients are allowed adaption of their on-going psychiatric treatments after week 20 but also earlier if the treating physician deems this necessary.

Biological and psychiatric assessments will be performed at pre-decided time points (see table 1). Patients will be followed by additional visits to a nurse for in-between visits.

Side effects will be monitored at each visit. Patients will continue their regular visits with the psychiatric staff.

At endpoint 1 (20 weeks) a separate interview lasting approximately 45 minutes will be held for a qualitative analysis.

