7.2 Study Termination

Patients may withdraw from the study at any time, of their own choice or by investigator decision, due to safety reasons or in case the patient is not able to comply with the protocol. Data collected up to the end of follow-up will be used in the final analysis of the study. If a patient wants to discontinue the study participation, data collected until that time point will be analysed in the study.

Early termination of the study may occur due to decision of regulatory authority or ethics committee, safety issues or sponsor decision. The study is completed when the last patient has done their last study visit.

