8.2 Administration of study drugs

A MabThera dose of 1000 mg will be given as intra-venous infusion in 1000 ml physiological saline (0.9 %, any brand provided by the pharmacy). Before administration of MabThera all patients will be given pre-medication to prevent or reduce possible side effects from MabThera.

Premedication is delivered 1-2 hours prior to rituximab and consists of T. Paracetamol 1000 mg, T. Loratadine 10 mg and T. Betapred (Betamethasone) 0.5 mg x 12 p.o (dissolved in a glass of water) in order to reduce the incidence of infusion-related reactions.

Patients remain on their stabilized treatments with psychotropic drugs during the first phase (20 weeks) of the study.

MabThera will be administered on one single occasion.

The MabThera treatment is administrated at the Rheumatology clinic at Örebro University Hospital. Study staff at the department of Rheumatology will prepare the saline bag for each patient infusion, adding MabThera. All bags will be labelled with a study specific label (**Error! Reference source not found.**). Each bag for infusion will be prepared just in time for each visit.

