9 ADVERSE EVENT, AE AND SERIOUS ADVERSE EVENT, SAE

9.1 Adverse Events, AE

An Adverse Event (AE) is any untoward medical occurrence in a patient/healthy volunteer administered a pharmaceutical product and which does not necessarily have to have a causal relationship with that treatment or usage. An AE can therefore be any unfavourable and unintended sign (including an abnormal laboratory finding), symptom or disease temporally associated with the use of a medical (investigational) product, whether or not related to the product.

Patients will be asked if they have experienced any AE by means of the following questions, administered at each visit:

- Have you noticed any new symptoms or problems since your last visit? If yes, which?
- Do you gather these symptoms can be related to a rituximab treatment?
- Have you noticed if any of your previous side effects have attenuated or increased? If yes, which ones?

We will also ask questions on specific adverse events that have been documented to be associated with rituximab treatment at each visit using the AAR. In addition, specific AEs, relevant for psychiatry, will be checked with the UKU Side Effect Rating Scale at **endpoint 1 and 2**.

The sponsor, as principal investigator or any investigator delegated to work in the study will record any AEs and assess the seriousness and severity (mild, moderate, severe) and whether the AE is related to the study medication. All investigators delegated to work in the study will report AEs to the principal investigator who is the sponsor in this study.

All AEs that are observed from the time of the administration of study medication until the patient leaves the study will be registered, analysed and summarized at the end of the study. Only serious adverse events will be recorded in the medical record.

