9.2 Serious Adverse Event, SAE

Each adverse event is to be classified by the investigator as serious or non-serious. An adverse event that meets one or more of the following criteria/outcomes is classified as serious:

- Results in death
- Is life-threatening, i.e., the patient was, in the opinion of the Investigator, at immediate risk of death from the event as it occurred (It does not include an event that, had it occurred in a more severe form, might have caused death.)
- Results in persistent or significant disability/incapacity
- Requires in-patient hospitalization or prolongs hospitalization
- Is a congenital anomaly/birth defect
- Is another medically significant event that, based upon appropriate medical judgment, may jeopardize the volunteer and may require medical or surgical intervention to prevent one of the outcomes listed above (e.g., allergic bronchospasm requiring intensive treatment in an emergency room or home, blood dyscrasias or convulsions that do not result in hospitalization, or the development of drug dependency or drug abuse)

SAE that occurs during the study will be documented and reported to sponsor within 24 hours after the investigator is aware of the SAE. SAEs will be documented, analysed and summarized at the end of the trial. SAE will be followed until the participation in the trial is ended or they are resolved.

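### Rituximab is given once, so removing a patient for safety after the infusion withdraws no drug, but it ends AE registration and lets SAE follow-up stop unresolved

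*Combined protocol and SAP*

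**What the plan says.** **Dosing and follow-up.** Section 8.2: "MabThera will be administered on one single occasion". Section 7.1: "All patients will be treated with the study drug rituximab on one single occasion and followed for a total of 1 year".

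**Removal.** Section 6.3: "The investigator can remove a patient from the study due to safety reasons". Inability to comply with the protocol is the other ground it gives. Section 7.2 repeats this: "Patients may withdraw from the study at any time, of their own choice or by investigator decision, due to safety reasons". Neither section defines a status in which a patient has finished or stopped treatment but stays in follow-up.

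**Safety record.** Section 9.1: "All AEs that are observed from the time of the administration of study medication until the patient leaves the study will be registered". Section 9.2: "SAE will be followed until the participation in the trial is ended or they are resolved".

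**Use of data.** Section 6.3 uses the data gathered before the patient left. Section 7.2 says "Data collected up to the end of follow-up will be used in the final analysis of the study", then limits patients who choose to discontinue to data gathered by that time. Section 10.2.1 analyses clinical data in a modified ITT set that includes dosed dropouts.

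**Schedule.** Tables 1 and 2 list no early-termination visit and no assessment after removal.

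**Purpose.** Section 5.1 makes safety and tolerability an objective. Section 12.3 says that the frequency of depression and nervousness as side effects of rituximab is unknown in psychiatric patients.

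**The concern.** In a trial with repeated dosing, taking a patient off for safety stops further exposure, and that benefit can be weighed against lost follow-up. Here the only dose has already been given. After the infusion, removal from the study has no protective effect through the drug. Its effects are to close AE registration, to permit an open SAE to be dropped, and to take the patient off the rating schedule.

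The patients affected are those in whom the investigator saw a safety problem. In a first trial of the drug in this population, with 12 patients, each one is 1/12 = 8.3% of the safety experience. The protocol itself treats the year after dosing as relevant: side-effect checks run to week 52 (Table 1), B cells are retested at week 52 if not normal at week 40 (section 7.1.3), and contraception is required for 12 months after treatment (section 6.1).

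**Working it through.** The plan states no figure on this point, so there is nothing to reproduce. The check has three steps: read the rules together, count what a removal loses, and cost what the fix restores.

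**1. The rules together.** One infusion (7.1, 8.2) means that no drug is left to withdraw afterwards. Removal is from the study (6.3, 7.2). AE registration ends on leaving the study (9.1). SAE follow-up has two permitted end points, the end of participation or resolution (9.2), so it can stop with the event unresolved. No later visit is scheduled (Tables 1 and 2). Together these end the safety record at removal.

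**2. Scheduled assessments after the infusion.** Weeks are taken from Table 1 and section 7.1.3, because the columns of Table 2 are displaced in the text available.
- Side-effect checks: weeks 2, 5, 8, 12, 16, 20, 24, 32, 40, 52 = 10
- PANSS: weeks 12, 20, 40, 52 = 4
- UKU: weeks 20, 40 = 2
- B-cell samples: weeks 5, 12, 20, 40 = 4 (week 52 conditional)

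Lost = assessments scheduled after the removal week. AE window = removal week / 52.

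| Removed just after | Side-effect checks lost | PANSS lost | UKU lost | B-cell samples lost | AE window |
|---|---|---|---|---|---|
| Week 5 | 8 of 10 | 4 of 4 | 2 of 2 | 3 of 4 | 5/52 = 9.6% |
| Week 12 | 6 of 10 | 3 of 4 | 2 of 2 | 2 of 4 | 12/52 = 23.1% |
| Week 20 | 4 of 10 | 2 of 4 | 1 of 2 | 1 of 4 | 20/52 = 38.5% |

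These are losses per removed patient at illustrative weeks. The documents give no removal rate, so no trial-level loss follows.

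**3. Time to restore them.** Times from Table 2: PANSS 20, CGI-S 5, CGI-I 10 and PGE 5 min, so 40 min per full rating visit; side-effect check 10; UKU 10; blood sample 15. Table 1 also schedules PGE at the nurse visits in weeks 8, 16, 24 and 32, at 5 min each.

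Minutes = 40 × rating visits + 10 × side-effect checks + 5 × nurse-visit PGE + 10 × UKU + 15 × blood samples.
- After week 5: 4×40 + 8×10 + 4×5 + 2×10 + 3×15 = 160 + 80 + 20 + 20 + 45 = 325; with the conditional week-52 sample, 340
- After week 12: 3×40 + 6×10 + 3×5 + 2×10 + 2×15 = 120 + 60 + 15 + 20 + 30 = 245; with it, 260
- After week 20: 2×40 + 4×10 + 2×5 + 1×10 + 1×15 = 80 + 40 + 10 + 10 + 15 = 155; with it, 170

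**The case against.** **Removal is optional.** Sections 6.3 and 7.2 permit it and do not require it; the default is a year of follow-up. This stands, and it limits the size of the point. It does not change what happens when the option is used.

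**The wording leaves room.** Section 7.2 refers generally to the end of follow-up, and 9.2 does not say whichever comes first. Both could be read as letting follow-up continue. Neither overrides the explicit cut-off in 9.1, and neither creates a visit.

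**Other safeguards exist.** Section 9.3 keeps SUSARs arising during the trial reportable, and section 7.1 keeps patients on their regular psychiatric visits. The first covers only unexpected serious reactions. The second is routine care, which neither registers AEs nor rates PANSS.

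**Severe events stop the whole study.** Section 11.2 stops the study for a severe side effect such as PML, so individual removal may not be the operative rule for the worst events. This is correct, but the documents do not say how dosed patients are followed after such a stop, so the fix should cover it.

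**Many assessments are optional.** Sections 7.1 and 12.3 make only a few procedures mandatory. The counts above are therefore scheduled assessments, some of which a patient might decline anyway.

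**Stronger readings.** A reader might infer that the primary PANSS analysis is biased. The documents do not support that: they give no removal rate, and the main drug harms listed in section 12.3 are somatic, so removal need not be related to PANSS. Nor is a missing week-20 PANSS particular to this rule, since it can equally follow a missed visit or withdrawn consent. A reader might also infer that the sentence in 12.3 on discontinuing the study drug leaves later depression or anxiety without any action. It does not, because section 7.1 says "Patients are allowed adaption of their on-going psychiatric treatments after week 20 but also earlier if the treating physician deems this necessary" and 12.3 also allows doses to be adapted. That sentence is at most leftover wording.

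**Conclusion.** The point holds in a limited form. Applied as written, the plan shortens the safety record of patients removed for safety at a stage when removal can no longer reduce exposure, and it allows an SAE to go unfollowed before it resolves. This is a consequence of stated rules, and it works against a stated objective.

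The size is known only per removed patient: after week 5, for example, 8 of 10 side-effect checks and 4 of 4 post-dose PANSS ratings are lost, with AEs registered for 5 of 52 weeks. The conclusion rests on removal happening after the infusion is complete, and on reading 9.1 as applying to a patient whom the investigator has removed, which is its plain sense. It does not rest on how long the drug acts; section 4.1 calls the effect reversible and gives no duration. The sponsor should make the change, because it is cheap and concerns participant safety, but nothing here shows that any patient will be removed.

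**What to change.** 1. **Sections 6.3 and 7.2.** State that removal for safety after the infusion does not end follow-up. Unless the patient withdraws consent to follow-up, or the investigator judges a particular assessment unsafe, the scheduled side-effect checks and PANSS, CGI and PGE ratings continue to week 52, with UKU and B-cell samples where the patient agrees. Patients removed only for inability to comply keep AE checks where feasible. The same safety follow-up applies to dosed patients if the study is stopped under 11.2.
2. **Section 9.1.** Register AEs until week 52 or withdrawal of consent to follow-up, including after removal by the investigator.
3. **Section 9.2.** Follow each SAE until it is resolved or stable, even if participation ends first, unless consent is withdrawn.
4. **Section 10.2.1.** Include ratings obtained after removal in the modified ITT analysis, and report the number, week and reason of removals.

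The discontinuation sentence in 12.3 can be tidied at the same time; nothing depends on it.

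**Cost.** Wording in five sections (6.3, 7.2, 9.1, 9.2 and 10.2.1), with no new scale and no new scheduled visit. Assessment time per removed patient is 325 to 340 min after week 5, 245 to 260 min after week 12 and 155 to 170 min after week 20, plus any contacts for SAEs followed beyond week 52. Some patients will decline, so the gain is partial.

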9.2 Serious Adverse Event, SAE

Each adverse event is to be classified by the investigator as serious or non-serious. An adverse event that meets one or more of the following criteria/outcomes is classified as serious:

- Results in death
- Is life-threatening, i.e., the patient was, in the opinion of the Investigator, at immediate risk of death from the event as it occurred (It does not include an event that, had it occurred in a more severe form, might have caused death.)
- Results in persistent or significant disability/incapacity
- Requires in-patient hospitalization or prolongs hospitalization
- Is a congenital anomaly/birth defect
- Is another medically significant event that, based upon appropriate medical judgment, may jeopardize the volunteer and may require medical or surgical intervention to prevent one of the outcomes listed above (e.g., allergic bronchospasm requiring intensive treatment in an emergency room or home, blood dyscrasias or convulsions that do not result in hospitalization, or the development of drug dependency or drug abuse)

SAE that occurs during the study will be documented and reported to sponsor within 24 hours after the investigator is aware of the SAE. SAEs will be documented, analysed and summarized at the end of the trial. SAE will be followed until the participation in the trial is ended or they are resolved.

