6 SELECTION AND WITHDRAWAL OF VOLUNTEERS

6.1 Inclusion Criteria

To be eligible for inclusion into this study, each patient must fulfil all of the following criteria:

- 1) Age: 18 to 40 years
- 2) Duration of psychiatric illness: exceeding 2 years
- 3) Rated "Markedly ill", "Severely ill" or "Among the most extremely ill patients" on the Clinical Global Impression – Severity scale (CGI-S)
- 4) Global Assessment of Functioning below 50
- 5) Current diagnosis according to Diagnostic and Statistical Manual for Mental Disorders, 5th edition (DSM-5) of SSD (schizophrenia spectrum disorder)
- 6) Treatment resistance, i.e. failing to remit despite adequate treatments
- 7) If female and with any risk for pregnancy: willing to use contraceptives.
- 8) If antipsychotic treatment is prescribed the plasma concentrations of the drug must be tested and shown to be within the therapeutic interval.
- 9) Subjects should be judged by the investigator to be lucid and oriented to person, place, time, and situation when giving the informed consent.
- 10) Immunoglobulin levels within the normal range

Treatment resistance is defined as poor general functioning (GAF<50) and minor or no persistent improvement from previous treatment attempts, according to the following specifications: At least 2 trials with different evidence-based drug treatments for schizophrenia and at least one from the second generation of anti-psychotic drugs. Both drugs should have been tested for a minimum of 4 months with adequate dosages. Clozapine must have been tested or considered not feasible

Fertile women will only be included in the study if they are using/agree to use adequate contraception during treatment with the study drug and for the following 12 months after the last treatment. Adequate contraception is defined as at least 1 of the following: 1) abstinence, 2) oral contraceptive (combined or progesterone alone), 3) implants of levonorgestrel, 4) estrogenic vaginal ring, 5) percutaneous contraceptive patches, 6) injectable progestogen, 7) intrauterine device (IUD) or 8) male partner sterilization. Non-fertile women are defined as any female that is surgically sterile (documented hysterectomy and/or bilateral oophorectomy or tubal ligation).

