7.1.3 Biochemical and other measures

There is still insufficient knowledge concerning inflammatory/immunological mechanisms of psychiatric disorders. Therefore, in order to increase our understanding and to extend the interpretational potential of clinical findings from our exploratory study, we will assess relevant immunological parameters, autoimmune biomarkers, genetic SNPs, etcetera. Additionally, we will apply routine safety biochemistry, recommended for rituximab in clinical use.

Also all subjects will be asked if they have received standard vaccinations and if they have had chicken pox, i.e. immunity to Varicella zoster (positive antibodies if unknown). If not then vaccinations must precede the treatment with rituximab.

Tests in blood and cerebrospinal fluid (CSF)

Blood and CSF will be drawn at baseline (before intervention), and at week 20 (after intervention). Analyses will include:

Blood only

At baseline, week 20 and week 40:

- Routine clinical tests for basic haematology, 5-partsdiff including neutrophil and lymphocyte count to be able to make the neutrophil/lymphocyte ratio and platelet counts, glucose, infection, liver function, renal function, electrolyte balance, thyroid status, 25-OH-vitamin D, PTH, vitamin B12, folat
- Expression levels of selected pro-inflammatory genes (e.g. IL-1 β , caspase, IL-6, IL-8), analysed using real-time PCR and DNA microarray technology

At baseline and week 20:

- Biomarkers for gut permeability (e.g. I-FABP, GLP-2)

At baseline, week 5, 12, 20, and 40:

- B-cell populations monitoring, by flow cytometric phenotyping (e.g. CD19, CD24, CD27, CD38, CD5), to quantify the impact of rituximab treatment (*if not normalized in week 40 a repeated test will be made in week 52*)

Routine clinical tests for 5-partsdiff including neutrophil and lymphocyte count to be able to make the neutrophil/lymphocyte ratio and platelet counts. *Only at prescreening/baseline:*

- Serology for hepatitis B, C and HIV
- QuantiFERON test (interferon- γ release assay) to check for response to *Mycobacterium tuberculosis*
- Drug concentration of psychotropic medication
- Assessment of autoimmune reactions against cerebral antigens (whole blood sample, stored in – 80° C) (application of novel findings from our group)

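### AE registration, and on one reading SAE follow-up, stops when a patient leaves the study, so removal for safety ends the trial's safety data collection but not exposure to the single dose

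*Combined protocol and SAP*

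**What the plan says.** Section 9.1 sets the adverse event window: "All AEs that are observed from the time of the administration of study medication until the patient leaves the study will be registered". Section 9.2 sets the window for serious events: "SAE will be followed until the participation in the trial is ended or they are resolved". It does not add whichever comes first or whichever comes later.

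On removal, section 6.3 states "The investigator can remove a patient from the study due to safety reasons", and section 7.2 repeats the option: "Patients may withdraw from the study at any time, of their own choice or by investigator decision, due to safety reasons". On data after that point, section 6.3 says "Data collected up to the subject's leaving the study will be used in the analysis of the study".

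Sections 7.1 and 8.2 describe one infusion per patient, and section 7.1 plans one year of follow-up. Section 7.1.3 schedules B-cell monitoring at weeks 5, 12, 20 and 40 and adds "if not normalized in week 40 a repeated test will be made in week 52". Safety and tolerability is an objective in section 5.1 and an outcome in section 5.2.

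**The concern.** In a repeated-dose trial, stopping treatment at least limits further exposure. Here the whole dose has been given before any removal can happen, so taking a patient out of the study changes only what the trial records.

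Taken together, the removal and AE rules let a harm close the observation window of the patient who had it. Length of follow-up then depends on the outcome being measured. In a 12-patient study with a safety objective, the AE summary would be thinnest for the patients about whom most needs to be known: how the event ended, and whether anything followed it.

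**Working it through.** The plan states no figure on this point, so the check is mainly a comparison of sections, followed by simple arithmetic on assumed removal times.

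1. **Is removal for safety the same as leaving the study?** Sections 6.3 and 7.2 both speak of leaving the study itself. Neither defines a status in which study visits stop but safety follow-up continues. No early-termination visit or post-withdrawal contact appears there, in sections 9.1 to 9.3, or in Tables 1 and 2.

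2. **Can removal reduce exposure?** No further dose is planned after the single infusion (sections 7.1 and 8.2). Section 12.3 says discontinuing the study drug should be considered if a patient becomes depressed or severely anxious, but after a completed infusion no dose remains to discontinue.

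3. **What happens to AE registration?** Under section 9.1 it ends on leaving. This wording has only one reading.

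4. **What happens to SAE follow-up?** Section 9.2 has two readings. If the earlier end point governs, follow-up of an unresolved SAE ends at removal. If the later one governs, the SAE is followed to resolution. The first reading matches section 9.1, but the text does not settle it.

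5. **What is still captured?** The event that prompts removal happens before the patient leaves. It is therefore registered, and if serious it is reported to the sponsor within 24 hours (section 9.2). What need not be captured is its later course and any new event.

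6. **How much could be lost?** Planned follow-up is 52 weeks (section 7.1, Table 1). The removal week r is an assumption, because the documents give none. Weeks lost = 52 − r:
   - r = 2: 52 − 2 = 50 weeks (50/52 = 96%)
   - r = 5: 52 − 5 = 47 weeks (47/52 = 90%)
   - r = 12: 52 − 12 = 40 weeks (40/52 = 77%)
   - r = 20: 52 − 20 = 32 weeks (32/52 = 62%)

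   Against the whole study, 12 × 52 = 624 patient-weeks. One such removal costs between 32/624 = 5.1% and 50/624 = 8.0% of planned safety observation. One patient is 1/12 = 8.3% of the sample.

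7. **In scheduled contacts (Table 1, section 7.1.3):** a patient removed just after the week 5 visit misses eight side-effect contacts (weeks 8, 12, 16, 20, 24, 32, 40 and 52). The B-cell tests at weeks 12, 20 and 40 are also missed, as is week 52 if it would have been triggered.

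8. **Study stop.** Section 11.2 says the study is stopped if any patient develops a severe side effect such as PML. It does not say how patients already dosed are then observed, so the same gap could apply to all of them at once.

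**The case against.** Several points on the other side are sound and limit the claim.

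- **The SAE sentence is ambiguous.** A reader might infer that SAE follow-up definitely stops at removal. Section 9.2 does not say so; the later-of reading would follow the event to resolution. Only the AE rule in section 9.1 is clear-cut.
- **The triggering event is not lost.** It is documented and summarised; only its outcome and later events are at risk.
- **Patients are not left without care.** Regular psychiatric visits continue (section 7.1), SAEs are entered in the medical record (section 9.1), and fatal or life-threatening SUSARs carry a follow-up report within a further 8 days (section 9.3). What ends is collection by the trial. None of these replaces it: the SUSAR rule covers only a narrow class of events, and routine visits are not described as a source of AE data.
- **Removal is optional.** Section 6.3 permits it and no SAE requires it. Section 7.2 can also be read as cutting data only for patients who choose to stop, since it separately uses data up to the end of follow-up. Section 6.3 leans the other way, so this is an inconsistency to resolve. The modified intention-to-treat rule in section 10.2.1 keeps dropouts in the analysis but creates no data after they leave.
- **Voluntary withdrawal is different.** The link between harm and lost follow-up is direct only for investigator removals for safety. Where consent is withdrawn, some loss cannot be avoided.
- **Duration of depletion is not stated.** A reader might infer from the contraception rule, "for the following 12 months after the last treatment", and the conditional week 52 test that depletion lasts about a year. The documents support less: section 4.1 says only that B cells eventually recover, and section 7.1.3 allows for counts not yet normal at week 40.

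The consent pages and the supplementary infusion routines were not available, so it cannot be confirmed whether either covers contact after withdrawal.

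**Conclusion.** The concern holds in a limited form. As written, section 9.1 ends AE registration when a patient leaves, section 9.2 can be read as doing the same for SAE follow-up, and no section available for review provides safety contact after removal. With a single dose and a one-year follow-up plan, a safety removal shortens trial safety data without shortening exposure, and it does so because of harm.

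The size depends on assumed removal times: 32 to 50 of 52 weeks for a patient removed between weeks 20 and 2. The documents give no removal rate, so no expected number of missed events can be calculated, and a claim that late infections would be understated by a given amount has no support. Nor do the documents show that depletion persists for any stated period. Even so, the change is worth making: it protects a stated outcome and the interests of patients already dosed.

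**What to change.** - **Section 9.1:** register AEs for every dosed patient from infusion to week 52, whether or not study visits continue, unless consent is withdrawn. For patients who stop visits, use the AAR by telephone at the scheduled contacts, or medical-record review, carried out by existing staff with the patient's consent. Because section 9.1 places only serious events in the medical record, the telephone AAR is the better source for non-serious ones.
- **Section 9.2:** follow each SAE until it is resolved, stable or otherwise explained, including after the patient has left the study.
- **Sections 6.3 and 7.2:** state that removal for safety ends study visits but not AE and SAE collection, and align the data-use sentences in the two sections.
- **Reporting:** present AEs with weeks of follow-up per patient, so that shortened observation is visible.
- **Reconciliation:** sections 6.3, 7.1.3, 7.2, 9.1, 9.2 and 11.2 should agree on what is observed after a removal or a study stop, including whether the B-cell tests apply. That clinical decision belongs to the sponsor and investigator; no rule is proposed here.

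The cost is protocol wording, matching consent text if it is not already there, and a few calls or record checks. Slightly more AEs may be reported.
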